Clinical Research Abstract

Brief Title	Study on the Correlation Between Treg Immune Cells on the Muscle Content and Cognitive Functions of the Elderly
ID	ZDWY.LNBK.007
Sponsor	Fifth Affiliated Hospital, Sun Yat-Sen University
Research unit	Fifth Affiliated Hospital, Sun Yat-Sen University
Main researcher	[name]
Statistical unit and person in charge of statistics	Fifth Affiliated Hospital, Sun Yat-Sen University [name]
Research purposes	In order to explore the impact of the level of the elderly TREG immune cells and the effects of different fat distribution and muscle content, the impact of the level of TREG immune cells on cognitive functions is explored. The correlation between visceral fat content, subcutaneous fat content and cognitive function.
Sample size	100
Study Type	Observational
Selected standards for subjects	
Inclusion criteria:
 
1. 40-90 years old
 
Exclusion criteria:
 
previous diagnosis of dementia (including Alzheimer's disease, Lewy body dementia, Parkinson's disease, or other dementias) were excluded.

Research step	
1. Collect 2023-05-01 to 2024-12-31 Elderly patients who are consulting in our hospital at the same time improve the data measurement and TREG cell measurement data at the same time; 2. The level of TREG immune cells and different fat distribution and muscle content Impact; 3. The impact of the level of TREG immune cells on cognitive function; 4.

	Evaluate the effects of different fat distribution and muscle content on cognitive functions, evaluate the correlation between internal organs, subcutaneous fat content and cognitive functions; 5. Write the paper.
Terminal indicator	Cognitive function decline
Statistical Analysis	Use a linear regression model to analyze the level of the level of TREG immune cells, the effects of different fat distribution and muscle content; the impact of the level of TREG immune cells on the level of TREG immune cells is analyzed by the Mann-Whitney U test; the evaluation of different fat distribution and muscle content The impact on cognitive functions, evaluate the correlation between the content of visceral fat, subcutaneous fat content and cognitive functions. Statistical software includes SPSS27 and Graphpad Prism 8. Inspection level $\alpha = 0.05$.

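### Hospital attenders are enrolled on age alone with only dementia excluded, and the apparent Treg–cognition test cannot adjust, so illness or drug states could produce a spurious association

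*Protocol*

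**What the plan says.** The protocol is a short synopsis. Under Study Type the design is given as "Observational". Step 1 of Research step takes the sample from "Elderly patients who are consulting in our hospital". Selected standards for subjects has one inclusion criterion, "40-90 years old", and one exclusion, a "previous diagnosis of dementia". Nothing restricts or stratifies by reason for attending, acute illness, comorbidity or medication. The planned number is 100.

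The endpoint under Terminal indicator is "Cognitive function decline". Statistical Analysis names three things:

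- a linear regression ("Use a linear regression model") relating Treg level to fat distribution and muscle content, with no covariates listed;
- a comparison that "is analyzed by the Mann-Whitney U test", in a sentence that names Treg level on both sides; step 3 of Research step suggests that Treg against cognition is meant;
- correlations of visceral and subcutaneous fat with cognition.

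The level of significance is 0.05. Sidedness is not stated.

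**The concern.** The exposure of interest is an immune-cell level, and the people in whom it is measured are attending a hospital. Acute infection, systemic steroids or immunosuppressants, active malignancy and autoimmune disease are all compatible with the eligibility rules. Each could plausibly move Treg level and also bear on cognitive performance or muscle content. A common cause of two variables induces an association between them even if neither affects the other.

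The protocol states its aims in terms of the impact and effects of Treg level. If the main Treg–cognition result is an unadjusted two-group comparison, it could reflect only which patients were ill or on such drugs when they were measured. Analysis cannot correct this afterwards if the conditions were not recorded, which is why it belongs in the data-collection step and not only in a later analysis plan.

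**Working it through.** **Inputs from the protocol.** N = 100 and alpha = 0.05 (taken as two-sided). The protocol gives no effect size, standard deviation or power, so there is no figure of its own to reproduce.

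**Inputs assumed.** A yes/no illness or drug factor has prevalence p of 10%, 20% or 30%. It lowers both Treg level and the outcome (cognition or muscle) by d = 0.5, 0.8 or 1.0 SD, and there is no true link between the two.

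**Induced correlation.** With unit variance within groups, the factor adds covariance p(1−p)d² and the same amount to each variance, so

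r = p(1−p)d² / [1 + p(1−p)d²].

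- p = 0.1, d = 0.5: 0.0225 / 1.0225 = 0.022
- p = 0.2, d = 0.8: 0.1024 / 1.1024 = 0.093
- p = 0.3, d = 1.0: 0.21 / 1.21 = 0.174

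**False-positive rates.** 4,000 simulated studies per row. Mann-Whitney compares Treg between patients below and above the median of the outcome. The median split is a further assumption, because the protocol does not say how its two groups are formed. The last column is a regression of the outcome on Treg adjusted for the factor.

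| p | d (SD) | Induced r | Unadjusted regression | Mann-Whitney | Adjusted regression |
|---|---|---|---|---|---|
| 10% | 0.5 | 0.022 | 5.5% | 5.0% | 5.1% |
| 10% | 0.8 | 0.054 | 8.6% | 6.8% | 4.9% |
| 10% | 1.0 | 0.083 | 13.2% | 8.2% | 4.8% |
| 20% | 0.5 | 0.038 | 6.5% | 6.5% | 5.1% |
| 20% | 0.8 | 0.093 | 15.0% | 11.0% | 5.0% |
| 20% | 1.0 | 0.138 | 28.7% | 17.8% | 4.6% |
| 30% | 0.5 | 0.050 | 8.6% | 6.6% | 5.6% |
| 30% | 0.8 | 0.118 | 21.4% | 15.4% | 5.2% |
| 30% | 1.0 | 0.174 | 39.5% | 27.0% | 4.6% |

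Simulation error is small: sqrt(0.05 × 0.95 / 4000) = 0.3 percentage points near 5%.

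**Cross-check.** For p = 0.2 and d = 1.0, Fisher's z gives atanh(0.138) × sqrt(97) = 1.37. The rejection rate is then Φ(1.37 − 1.96), about 27.7%, against 28.7% simulated.

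**With no shared factor (d = 0).** The unadjusted rates are 5.0–5.3%. This also represents leaving affected patients out.

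**Scale.** The correlation that N = 100 detects with 80% power is tanh[(1.960 + 0.842) / sqrt(97)] = 0.28. An induced r of 0.17 is well over half of that; 0.02 is trivial beside it.

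**The case against.** The strongest reply is that this is an absence in a synopsis of a few lines. The document lists no data fields at all, so one cannot conclude that diagnoses and medication will go unrecorded. Covariate lists and sensitivity analyses are commonly left to a SAP, and none is shown. This stands in part: the covariates of the linear regression may be settled elsewhere. It does not cover the whole point. The protocol itself fixes the source population, the eligibility and a test that cannot take covariates, and an analysis plan cannot adjust for what was not collected.

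Second, the causal premise and every magnitude come from outside the document. Consulting a hospital does not establish acute illness, and nothing says how common these states are here. This stands. In addition, the model gives several different conditions one common shift in one direction. If directions or sizes differ, the induced correlation shrinks or cancels. The return to about 5% after adjustment was obtained under the same single-factor model.

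Third, a reader might infer that no planned analysis could deal with the problem. The document does not support that: the regression for fat and muscle can carry covariates. A reader might also infer a single blood draw of circulating cells, but the protocol states neither the sample nor the number of measurements.

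**Conclusion.** The concern holds as a design weakness of unknown size. Eligibility by age with only dementia excluded, combined with an apparently unadjusted Treg–cognition test, leaves plausible common causes uncontrolled if the plan is followed as written.

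Under the assumed ranges the false-positive rate goes from about 5% to 27% for Mann-Whitney and about 40% for unadjusted regression. The effect is negligible if the factor is rare or weak, and material if it is common and strong. The larger regression figures should not be read as applying to Mann-Whitney, whose rate was no higher in any scenario and clearly lower in most.

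A reader might infer that any Treg–cognition finding from this study would be spurious. The document does not support that, since it gives neither prevalence nor effects. The conclusion also rests on reading the garbled Mann-Whitney sentence as the Treg–cognition comparison, as step 3 suggests. The change is worth making because it is cheap and the data are hard to recover later.

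**What to change.** 1. In step 1 of Research step, add chart fields as at the time of the Treg measurement: acute infection or other acute illness, systemic steroid or immunosuppressant use, active malignancy, and autoimmune disease.
2. Make a regression of cognition on Treg level, adjusted for these, the main Treg–cognition analysis, and keep Mann-Whitney as descriptive. This is a change of analysis and not just an added covariate, because the protocol names no Treg–cognition regression.
3. Add the same covariates to the planned regression of Treg level with fat distribution and muscle content.
4. Enter the conditions as separate indicators where numbers allow, otherwise as one pooled yes/no indicator.
5. Pre-specify a repeat of these analyses excluding affected patients as a sensitivity analysis.

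The cost is a few chart fields for each of 100 patients and a few degrees of freedom. The sensitivity analysis will have a smaller n. A pooled indicator may leave residual confounding, because it removes the bias fully only if the conditions act alike. Who is enrolled does not change.

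### The test apparently planned for Treg and cognition takes no covariates, so a Treg result could not be separated from a fat or muscle result

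*Protocol*

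**What the plan says.** The Research step row of the Clinical Research Abstract sets out three questions, each about one pair of variables:

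- Step 2: "The level of TREG immune cells and different fat distribution and muscle content Impact"
- Step 3: "The impact of the level of TREG immune cells on cognitive function"
- Step 4: "Evaluate the effects of different fat distribution and muscle content on cognitive functions"

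The Statistical Analysis row follows the same order. For the first question it says "Use a linear regression model to analyze the level of the level of TREG immune cells", together with fat distribution and muscle content. Next it says "the impact of the level of TREG immune cells on the level of TREG immune cells is analyzed by the Mann-Whitney U test". The third item, fat and muscle with cognition, has no named method. No covariate, stratification, matching or mediation analysis is mentioned. The study type is "Observational" and the age criterion is "40-90 years old".

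**The concern.** Steps 2 and 4 propose that fat and muscle are related to Treg and also to cognition. If both relations exist, fat and muscle stand between the two variables of step 3, either as common correlates or as part of a pathway. Where the relations point in compatible directions, Treg and cognition will then be associated even if nothing links them directly.

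The plan describes no analysis that contains Treg, body composition and cognition together. The study is not randomised, so nothing in the design balances fat and muscle across Treg levels. The Research purposes row places all of these variables in one objective and speaks of the *impact* of Treg on cognition. A significant step 3 result could be read as specific to Treg when Treg is only a marker of fat or muscle, and the planned tests could not tell the two apart.

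**Working it through.** **Which test belongs to step 3.** The Mann-Whitney sentence names Treg as both predictor and outcome, so it cannot be read literally. Linear regression is already given to Treg with fat and muscle, and the fat/muscle-cognition item follows separately. Treg with cognition is the only question left. This assignment is an inference. The Mann-Whitney U compares two groups and has no place for a covariate.

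**Size.** The protocol states no effect size, correlation, standard deviation or power, so there is no figure of its own to reproduce. The check below is an illustration.

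Inputs from the protocol: n = 100 and alpha = 0.05. Sidedness is not stated; two-sided is assumed.

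Assumed: one body-composition variable B, correlated r with Treg (T) and r with cognition (C), with no direct link:

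- T = r·B + √(1 − r²)·e₁
- C = r·B + √(1 − r²)·e₂

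B, e₁ and e₂ are independent standard normal, so the induced T–C correlation is r × r. Cognition is split into two groups, either 50/50 or 30/70. Treg is compared between the groups (i) by Mann-Whitney U and (ii) by linear regression of Treg on group plus B. There were 4,000 simulated studies per setting.

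| r with both | Induced correlation | Mann-Whitney, 50/50 | Mann-Whitney, 30/70 | With B in model, 50/50; 30/70 |
|---|---|---|---|---|
| 0 | 0 | 0.051 | 0.052 | 0.051; 0.056 |
| 0.2 | 0.04 | 0.060 | 0.055 | 0.045; 0.045 |
| 0.3 | 0.09 | 0.104 | 0.100 | 0.051; 0.052 |
| 0.4 | 0.16 | 0.237 | 0.203 | 0.047; 0.050 |
| 0.5 | 0.25 | 0.494 | 0.434 | 0.048; 0.049 |
| 0.6 | 0.36 | 0.810 | 0.774 | 0.051; 0.055 |

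Entries are shares of studies with p < 0.05. The Monte Carlo standard error near 0.05 is √(0.05 × 0.95 / 4,000) = 0.003.

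**Sensitivity to the number of compartments.** Suppose two independent compartments each correlate 0.3 with T and with C, in directions that add. The induced correlation is 2 × 0.09 = 0.18. For a correlation test, Fisher's z is atanh(0.18) × √97 = 0.182 × 9.849 = 1.79, and the probability of significance is Φ(1.79 − 1.96) = 0.43. The same setting tested by Mann-Whitney on a median split gives about 0.28. If the two compartments correlate 0.5 with each other, the induced correlation is 2 × 0.09 / 1.5 = 0.12, and the correlation test gives Φ(1.19 − 1.96) = 0.22. If the directions oppose and cancel, the rate returns to about 0.05.

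**The case against.** *The protocol is silent on adjustment, and silence may be filled by a statistical analysis plan that is not shown.* This is partly right. The step 3 wording is a research question and says nothing about covariates either way. The regression clause also names no clear outcome, so a joint model is not expressly excluded. But the protocol does name a test, and the only question left for that test is one where fat and muscle matter. What is fixed badly is the choice of method. The link to step 3 remains inferred.

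*The association is real.* A reader might infer that the step 3 test has an inflated false-positive rate, or that the study would be wrong to call Treg a correlate of cognition. The document does not support that. The title speaks of correlation and the purpose is to explore. If body composition induces an association, the marginal association exists, and a test that detects it is not making a type I error. The rates above show how often the unadjusted test would be significant with no direct link. They are errors only if the result is read as Treg-specific.

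*Fat and muscle may be pathway.* The protocol does not say whether they are confounders or mediators. If Treg acts through them, the unadjusted result is a valid total association. This stands, and it is why both models should be shown instead of replacing one with the other.

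*The size is driven by assumptions.* This also stands. A figure as high as 43% needs two independent compartments with additive effects and a correlation test. With one variable at 0.2 the excess is negligible.

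**Conclusion.** The point holds as a weakness in the choice of analysis. Read as written, and with the Mann-Whitney test assigned to step 3 by elimination, the plan can give a marginal Treg-cognition association but cannot say whether it goes beyond fat and muscle. Wording that implies a Treg-specific impact would not be supported.

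How much this matters is unknown from the document. With one body-composition variable and equal correlations, it is slight at 0.2, about double the 5% rate at 0.3, and large from 0.4 upwards. The return to about 5% after adjustment assumes that body composition enters linearly and is measured without error; measurement error would leave part of the induced association in place. Age, with eligibility from 40 to 90 years, can act in the same way and is not named in any analysis. The study can proceed, but the change is cheap and should be made.

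**What to change.** 1. Correct the Mann-Whitney sentence in the Statistical Analysis row so that it names cognition as the outcome.
2. For step 3, report two regressions of the cognitive measure on the same patients: linear if it is a score, logistic if it is dichotomised as decline yes/no.
   - (a) Treg, age and sex.
   - (b) The same plus visceral fat, subcutaneous fat and muscle content.
3. Give the Treg coefficient with its 95% confidence interval from both models. Claim an association beyond body composition only from (b), and word it as conditional, because fat and muscle may be pathway as well as confounder.

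**Cost.** No new patients are needed. Fat, muscle, Treg and cognition are already to be measured, and age is needed for eligibility; that sex is recorded is an assumption. The interval for Treg in (b) will be somewhat wider. In the one-variable linear setting above, the ratio of standard errors is about 1/√(1 − r⁴), which is 1/√0.9375 = 1.03 at r = 0.5. It is larger if fat and muscle predict Treg better than they predict cognition.

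Model (b) has six slopes. With a score that is 100/6, or about 17 patients per slope. With a dichotomised outcome the smaller group sets the limit: at an assumed 30/70 split, 30/6 = 5 per slope, which is thin and favours a score. In the logistic form, the change in the Treg coefficient from (a) to (b) should not be read as a measure of confounding, because odds ratios change on adjustment even without it.

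### The Mann-Whitney sentence relates Treg level to itself; read as Treg and cognition, step 3 rests on a test that cannot adjust for age in patients aged 40-90

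*Protocol*

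**What the plan says.** The protocol is a single abstract in table form. Its Statistical Analysis row states that "the impact of the level of TREG immune cells on the level of TREG immune cells is analyzed by the Mann-Whitney U test". The clause before it starts "Use a linear regression model to analyze the level of the level of TREG immune cells" and goes on to fat distribution and muscle content. The clause after it concerns "the evaluation of different fat distribution and muscle content The impact on cognitive functions" and mentions correlation without naming a test.

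Item 3 of the Research step row is "The impact of the level of TREG immune cells on cognitive function". The Research purposes row agrees: "the impact of the level of TREG immune cells on cognitive functions is explored". The Terminal indicator is decline in cognitive function.

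The study is observational, with 100 participants and alpha 0.05. The one inclusion criterion is "40-90 years old", and people with a "previous diagnosis of dementia" are excluded. Item 1 of the Research step row describes the source as "Elderly patients who are consulting in our hospital". No covariate, matching or stratification is mentioned anywhere.

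**The concern.** There are two parts. First, the sentence is wrong on its face: a variable cannot be tested for its effect on itself, and step 3 is left without a stated outcome.

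Second, once the sentence is read as it must be meant, the protocol fixes an unadjusted two-group comparison for a question about impact, in non-randomised patients whose ages may span 50 years. If Treg level and cognition both vary with age, they will be associated with each other even when neither affects the other, and the Mann-Whitney test cannot separate the two explanations. If the age effects run against a true link, the test can also hide it. Either way the result would not answer step 3, the question that ties Treg to the study's endpoint.

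**Working it through.** **1. What the sentence means.** The clauses of the Statistical Analysis row follow the order of the Research step row:

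| Clause | Method named | Variables as written | Research step |
|---|---|---|---|
| First | Linear regression | Treg; fat and muscle | 2 |
| Second | Mann-Whitney U | Treg; Treg | 3 (Treg; cognition) |
| Third | None beyond correlation | Fat and muscle; cognition | 4 |

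The second clause is therefore step 3, and the Research purposes row supports this. Mann-Whitney is the only method named for it.

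**2. Inputs.** From the protocol: N = 100, alpha = 0.05, ages 40-90. Assumed, because the protocol gives no values: two-sided testing, uniform ages, linear age effects, cognition split at the median, and the correlations with age. The protocol offers no figure to reproduce on this point; the sample size has no derivation and is not disputed here.

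**3. Model with no Treg-cognition link.** Let a = (age − 65)/(50/√12), e₁ and e₂ be independent standard normal, and r_T and r_C be the sizes of the correlations of age with Treg and with cognition over 40-90.

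- Treg = r_T·a + √(1 − r_T²)·e₁
- Cognition = −r_C·a + √(1 − r_C²)·e₂

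Age alone then induces a Treg-cognition correlation of size r_C·r_T. At 0.5/0.4 this is 0.5 × 0.4 = 0.20. For a narrower age range of width w, age variance shrinks by k = (w/50)² and the induced correlation is k·r_C·r_T / √[(1 − r_C² + k·r_C²)(1 − r_T² + k·r_T²)]. For ages 60-90, k = (30/50)² = 0.36, so 0.5/0.4 gives 0.072/√(0.84 × 0.8976) = 0.083. This is why the ages actually recruited matter so much.

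**4. False-positive rates.** Simulation with 10,000 replicates per setting (Monte Carlo error about 0.5 points). Mann-Whitney compares Treg between the low- and high-cognition groups.

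| r_C / r_T | 0.3/0.2 | 0.4/0.3 | 0.5/0.3 | 0.5/0.4 | 0.6/0.5 |
|---|---|---|---|---|---|
| Ages 40-90 | 8% | 16% | 23% | 38% | 73% |
| Ages 50-90 | 6% | 10% | 12% | 20% | 43% |
| Ages 60-90 | 6% | 7% | 8% | 10% | 19% |
| Ages 40-90, lowest 10% of cognition removed | 7% | 14% | 19% | 30% | 64% |
| Ages 60-90, lowest 10% of cognition removed | 5% | 6% | 7% | 8% | 16% |

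The last two rows mimic the dementia exclusion. Removing the lowest 20% instead gives 6, 12, 16, 25, 54% (40-90) and 5, 6, 7, 8, 14% (60-90). Splitting cognition at 25% rather than the median gives 7, 14, 18, 31, 61% at ages 40-90. In the tabulated and 20%-removed settings, regression with Treg and age stays at 4.6-5.5% (linear) and 4.4-5.3% (logistic). With r_T = 0, Mann-Whitney gives 4.3-5.5%, as it should.

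**5. Missing a true link.** Take a true Treg effect of +0.3 SD, with age lowering cognition and raising Treg. Power, Mann-Whitney against age-adjusted logistic regression on the same split:

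| Direct age effect on cognition / r_T | Ages 40-90 | Ages 60-90 |
|---|---|---|
| 0.3/0.3 | 37% against 66% | 56% against 66% |
| 0.5/0.3 | 20% against 72% | 53% against 74% |

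**The case against.** The step 3 reading is an inference, and the whole row is garbled, so the slip could lie on either side of the sentence. That is fair as to which word is wrong, but either repair pairs Treg with cognition and leaves the test unadjusted.

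Covariates are often left to a SAP, which is not shown here, and naming Mann-Whitney does not forbid an adjusted analysis. This limits the point without removing it: the protocol is not silent but positively names an unadjusted test for this question. The neighbouring regression also lists no covariates, but a regression can take age and a two-group rank test cannot.

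The strongest objection is that the harm is wholly conditional. Every correlation is assumed. The protocol repeatedly calls its patients elderly, and at ages 60-90 four of the five settings give only 6-10%. The 73% figure needs strong correlations across the full 40-90 range. If only a marginal correlation were wanted, as the brief title might suggest, rejecting would not be an error; step 3, however, asks about impact. All of this stands as a limit on size.

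The Mann-Whitney groups are also undefined. The fix below settles that for the main analysis.

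**Conclusion.** The concern holds. The wording error is certain and needs no assumption. On the evident reading, step 3 has only an age-unadjusted test, which is also certain from the text.

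The size of the resulting bias is not known. It depends on age being related to both Treg and cognition and on the ages recruited: potentially large if they fill 40-90, small in most settings if the sample is mostly over 60. The simulations show that confounding is possible, not that it is present. This should be fixed; confidence is medium because the second part is conditional.

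**What to change.** Rewrite the sentence so that cognitive function is the outcome. Make the main step 3 analysis a regression of cognitive function on Treg level with age as a covariate: linear if a score is recorded, logistic if the binary decline outcome is kept. Retain Mann-Whitney as a descriptive comparison. Sex, education or other covariates are optional, if recorded.

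The cost is one sentence and one degree of freedom for a variable that eligibility already requires. At an assumed Treg effect of 0.3 SD with age unrelated to Treg, adjusted logistic regression has 66-77% power against 64-73% for Mann-Whitney on a median split (58-70% against 56-66% on a 25% split). Linear regression on a score has 86-95%, mostly because nothing is dichotomised.

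There is a downside. If age is related to Treg but has no direct effect on cognition (ages 40-90), adjusted logistic regression has about 54% against 66% at r = 0.5, where linear regression on a score has 75%. At r = 0.3 the loss is slight, 63% against 66%.

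### The only analysis sentence for the Treg and cognition aim tests Treg against itself, and correcting the noun alone leaves a test that cannot adjust for age

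*Protocol*

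**What the plan says.** All of this is in the Protocol's Clinical Research Abstract table.

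- **Research purposes:** "the impact of the level of TREG immune cells on cognitive functions is explored".
- **Research step, item 3:** "The impact of the level of TREG immune cells on cognitive function".
- **Terminal indicator:** "Cognitive function decline" is the only entry. No instrument, cut-off or grouping is given.
- **Statistical Analysis, first item:** "Use a linear regression model to analyze the level of the level of TREG immune cells, the effects of different fat distribution and muscle content".
- **Statistical Analysis, second item:** "the impact of the level of TREG immune cells on the level of TREG immune cells is analyzed by the Mann-Whitney U test".
- **Statistical Analysis, third item:** fat and muscle against cognition, with no test named.
- **Design:** observational, 100 patients, alpha 0.05. The only inclusion criterion is "40-90 years old".

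**The concern.** There are two parts, and they are not equally firm.

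The firm part is the wording. A variable cannot be tested for its effect on itself, and the aim that should stand at this point in the row has no other method. Cognitive decline is the only terminal indicator, and Treg with cognition is one of two aims that bear on it (the other is fat and muscle with cognition). An analyst following the text could not produce the result.

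The conditional part is what remains if only the noun is corrected. A plain Mann-Whitney test compares two groups and has no place for age. With patients from 40 to 90 and no randomisation, age may be related both to Treg level and to cognition. A positive result could then reflect age alone. If age pushes the two variables in opposite directions while the direct link is positive, a real association could be hidden.

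**Working it through.** **Step 1. Set the aims beside the analyses.**

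| Research step | Aim | Statistical Analysis item | Method named |
|---|---|---|---|
| 2 | Treg with fat and muscle | first | linear regression |
| 3 | Treg with cognition | second: Treg with Treg | Mann-Whitney U |
| 4 | fat and muscle with cognition | third | none |

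The first and third items fit steps 2 and 4, so by order the second belongs to step 3. It does not mention cognition, and no other item links Treg to cognition.

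**Step 2. Take the sentence literally.** Split 100 Treg values at their own median and compare Treg between the halves. Every value in the upper half exceeds every value in the lower half, so U = 50 × 50 = 2500, the maximum, and p is about 7 × 10⁻¹⁸ whatever the data. The result carries no information.

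**Step 3. Read it as cognition, with no direct Treg-cognition link.** From the Protocol: n = 100 and alpha 0.05. Assumed, because the Protocol is silent: a two-sided test, the group split (50:50 to 20:80), and the correlations of age with Treg (a) and with cognition (b). The Protocol does not derive its sample size, so there is no figure of its own to reproduce.

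Age alone induces a correlation r = a × b. For a 50:50 split on cognition, the mean shift of the Mann-Whitney z statistic is approximately

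δ = k × √(n − 3) × atanh(r), with k = √(2/π) × √(3/π) = 0.780.

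The first factor of k is the loss from splitting at the median and the second is the efficiency of the rank test. The rejection rate is P(Z > 1.96 − δ) + P(Z < −1.96 − δ).

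At a = b = 0.4: r = 0.16, √97 × atanh(0.16) = 1.589, δ = 0.780 × 1.589 = 1.24, giving a rejection rate of 0.236.

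Simulation (20,000 datasets per setting, normally distributed age) agrees:

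| a = b | r | Formula, 50:50 | Simulated 50:50 | 30:70 | 20:80 |
|---|---|---|---|---|---|
| 0.2 | 0.04 | 0.061 | 0.059 | 0.059 | 0.057 |
| 0.3 | 0.09 | 0.107 | 0.105 | 0.098 | 0.088 |
| 0.4 | 0.16 | 0.236 | 0.236 | 0.217 | 0.195 |
| 0.5 | 0.25 | 0.501 | 0.491 | 0.452 | 0.392 |

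- With age uniform on 40 to 90, the 50:50 rates at 0.3, 0.4 and 0.5 are 0.109, 0.257 and 0.549.
- Age-adjusted linear regression rejects in 0.049-0.052 throughout, and age-adjusted logistic regression (5,000 datasets) in 0.040-0.049.
- With no age correlation, Mann-Whitney rejects in 0.049-0.050. The test itself is sound.
- Unequal links, uniform age, separate simulation of 3,000 runs: 0.2 and −0.3 give about 7%; 0.3 and −0.4, 14-16%; 0.4 and −0.5, 32-38%.
- One weak link, 30:70: 0.1 and 0.3 give 5.3%; 0.1 and 0.5 give 6.4%.

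**Step 4. Masking.** Take a partial correlation of 0.277. This is chosen because it gives 80% power at n = 100: √97 × atanh(0.277) = 2.80, and 2.80 − 1.96 = 0.84, so the 80% is a benchmark and not evidence about this study. Let age raise Treg and lower cognition at 0.3 each. The marginal correlation falls to 0.277 × (1 − 0.09) − 0.09 = 0.162. Simulated power is 19-24% for Mann-Whitney, 47-59% for age-adjusted logistic regression and 80% for age-adjusted linear regression on a score.

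**Step 5. Power without confounding, r = 0.277.** Linear regression on an uncut score has 80% power, against 48-58% for Mann-Whitney on the split score. If the endpoint is truly yes/no, logistic regression has 49-59%, so regression then brings no power gain.

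**The case against.** The strongest reply is that this is one damaged noun. The same row also has "Use a linear regression model to analyze the level of the level of TREG immune cells", which is the same kind of damage, and the Research purposes and Research step rows show what was meant. Adjustment is normally left to a statistical analysis plan, which may exist and is not at hand, and the Protocol does not forbid it. The linear regression in the first item is silent on age too. An unadjusted comparison is legitimate in an exploratory study. Finally, every correlation above is assumed, and one weak age link brings the error rate close to 5%.

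Much of this stands. The slip is probably editorial, the age point is a limitation of the named test and not a contradiction, and its size is unknown. The power loss applies only if a score is cut into groups. Two things remain. The printed sentence is the current text, and an analysis plan that used cognition would depart from it. Correcting the noun also leaves the groups undefined: high against low Treg compared on cognition, or decline against no decline compared on Treg, are different analyses. As for the first item, a regression can take age as a covariate without changing method; a plain Mann-Whitney test cannot.

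**Conclusion.** The concern holds. As printed, the Treg and cognition aim has no executable analysis. This follows from the wording alone, needs no assumption, and must be corrected.

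The age argument is conditional and explains why the repair should go beyond the noun. With age correlations of 0.2 to 0.5 with both variables, the unadjusted test's false-positive rate runs from about 6% to about 55%, against about 5% for age-adjusted linear regression. It is close to nominal if either link is weak. These figures assume n = 100, a two-sided 0.05 level and a linear age relation.

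**What to change.** Replace the second item of the Statistical Analysis row with wording such as:

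> Treg level, as a continuous variable, is related to cognitive function, measured by [name the measure], in a regression adjusted for at least age: linear if the measure is a score, logistic if decline is recorded as yes or no. The estimate is reported with its 95% confidence interval. Further covariates, such as sex and education, enter only if collected. The Mann-Whitney U test serves as a descriptive comparison of Treg level between cognitive groups defined in advance.

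The cost is one row of text and naming the cognitive measure. Age is already needed for eligibility, SPSS 27 is already listed and fits both models, and no patients are added. The downside is slightly more analysis work and one degree of freedom per covariate.
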